11.2.1 Serious Adverse Experience Reporting

Study sites will document all SAEs that occur (whether or not related to treatment arm assignment) on an SAE Report Form. The collection period for all SAEs will begin after informed consent is obtained and end after procedures for the final study visit have been completed.

All SAE Report Forms will be reviewed by the site investigator and sent to the TDNCC within one business day of the site learning of the event. Sites will send the SAE report by either:

- Email (scanned copy) to: [contact]
- TDNCC SAE [contact]

The site will notify the TDNCC of additional information or follow-up to an initial SAE Report as soon as relevant information is available. The TDNCC Medical Monitor may request additional information related to the SAE. Follow-up information is reported on an SAE Report Form.

In accordance with the standard operating procedures and policies of the local Institutional Review Board/Independent Ethics Committee (IRB/IEC), the site investigator will report SAEs to the IRB/IEC.

12 DISCONTINUATION AND REPLACEMENT OF SUBJECTS

12.1 Early Withdrawal of Subjects from the Study

Early withdrawal of subjects may occur any time after the subject is randomized. All subjects are free to withdraw from participation at any time, for any reason, specified or unspecified, and without prejudice. This may include subjects who withdraw from study treatment early and who decline to continue to come in for remaining follow-up visits or it may include subjects who completed treatment and decline to come in for remaining follow up visits.

Reasonable attempts will be made by the investigator to provide a reason for early subject withdrawals. The reason for the subject's early withdrawal from the study will be specified in the subject's source documents.

Subjects who fail to adhere to treatment duration assignment are encouraged to complete all remaining study visits. Subjects should not be withdrawn for failure to adhere to treatment duration assignment.

12.2 Replacement of Subjects

Subjects who withdraw from the study will not be replaced.

13 PROTOCOL VIOLATIONS

A protocol violation occurs when the subject, investigator, or the Sponsor fails to adhere to significant protocol requirements affecting the inclusion, exclusion, subject safety and primary endpoint criteria. Protocol violations for this study include, but are not limited to, the following:

- Failure to meet inclusion/exclusion criteria
- Use of a prohibited concomitant medication
- Failure to adhere to treatment duration assignment (within the pre-specified margins of acceptable durations)
- Failure to perform spirometry at each study visit

Failure to comply with Good Clinical Practice (GCP) guidelines will also result in a protocol violation.

When a protocol violation occurs, it will be discussed with the investigator and a Protocol Violation Form detailing the violation will be generated. This form will be signed by a Sponsor representative and the Investigator. A copy of the form will be filed in the site's regulatory binder and in the Sponsor's files. The site will report the violation to their IRB/IEC in accordance with their IRB/IEC reporting requirements.

14 DATA SAFETY MONITORING

The Cystic Fibrosis Foundation DSMB will establish a Data Monitoring Committee (DMC) to review data relating to safety and efficacy, to conduct and review interim analyses, and to ensure the continued scientific validity and merit of the study, according to the Cystic Fibrosis Foundation DSMB Operations Manual and a DMC Charter created for this protocol. Details regarding the timing and content of the interim reviews are included in Section 15.6, Interim Analysis below, the DMC Charter developed in conjunction with the DMC, and the Statistical Analysis Plan.

SAEs will be monitored by the committee on an ongoing basis throughout the study.

15 STATISTICAL METHODS AND CONSIDERATIONS

A detailed Statistical Analysis Plan (SAP) will be written that will describe all analyses that will be generated for this study. All analyses will be performed using SAS[®] (SAS Institute, Inc., Cary, NC, USA) or R (R Foundation for Statistical Computing, Vienna, Austria). The SAP will contain any modifications to the analysis plan described below.

15.1 Data Sets Analyzed

The primary NERR analyses will be performed using an intent-to-treat (ITT) population, which is defined as all subjects randomized at Visit 2. The analysis for NERR will be repeated in the per-protocol (PP) population, which is defined as subjects in the ITT population who have no protocol violations as defined in Section 13. The primary ERR analyses will be performed using PP population; the analysis will be repeated in the ITT population.

Subjects who fail to adhere to treatment duration assignment are encouraged to complete all remaining study visits and will remain in the analyses population according to ITT.

Handling of missing data will be outlined in the SAP, including sensitivity analyses.

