1.4 Definition of the Analysis Populations

Enrollment and screening summaries will be generated using all screened participants. All compliance and safety analyses will be performed using an intent-to-treat (ITT) population, defined as all subjects randomized at Visit 2. The ITT population will also be used to generate all NERR primary efficacy analyses. The primary ERR analyses will be performed using per-protocol population (PP), defined as subjects in the ITT population who have no protocol violations.

2. Results

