2.5 Summary of Primary Efficacy Endpoint

The primary endpoint is the absolute change in percent predicted FEV₁ from Visit 1 (Baseline) to two weeks after scheduled completion of IV antibiotics (Visit 3). The primary endpoint is compared between treatment durations within ERR and NERR groups using Analysis of Variance (ANOVA) adjusted for dichotomous randomization strata: Visit 1 FEV₁, number of IV-treated exacerbations in prior year, location of IV administration by Visit 2, and use of systemic corticosteroids by Visit 2. The treatment effect for each group (ERR and NERR) (estimated via adjusted ANOVA least squares means) is presented along with corresponding 95% confidence intervals. Observed treatment effect and the 95% CI provide primary inference and evidence of non-inferiority, superiority, or lack thereof in both the ERR and NERR groups.

ERR Group (PP population): The non-inferiority of ERR-10 versus ERR-14 is tested against a 3.5 % predicted non-inferiority margin with a one-sided 0.025 level of significance.

NERR Group (ITT population): The superiority of NERR-21 versus NERR-14 is tested with a two-sided 0.05 level of significance.

The primary analysis for ERR is repeated in the ITT population, and the primary analysis for NERR is repeated in the PP population.

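### ERR non-inferiority is decided in the per-protocol set, ITT has no stated part in the decision, and outcome-related exclusions could bias the result in either direction

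*Protocol*

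**What the plan says.** Protocol 15.1 sets the hierarchy for ERR: "The primary ERR analyses will be performed using PP population; the analysis will be repeated in the ITT population". SAP 1.4 also makes PP primary for ERR, with PP "defined as subjects in the ITT population who have no protocol violations". SAP 2.5 adds: "The primary analysis for ERR is repeated in the ITT population, and the primary analysis for NERR is repeated in the PP population". Protocol 15.3 and SAP 2.5 take the estimated effect and its 95% confidence interval as the primary inference. For ERR that interval is therefore the PP one. Neither document gives a success rule that involves ITT or a rule for discordant results.

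PP membership depends on Protocol 13, whose list is open: "Protocol violations for this study include, but are not limited to, the following". Besides eligibility failures, the named items are:

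- "Failure to adhere to treatment duration assignment (within the pre-specified margins of acceptable durations"; the Synopsis gives ±1 day for both ERR arms
- "Use of a prohibited concomitant medication"
- "Failure to perform spirometry at each study visit"

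On missing data, Protocol 15.1 says: "Handling of missing data will be outlined in the SAP, including sensitivity analyses". The SAP text supplied describes no method.

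**The concern.** Randomization protects the ITT comparison. PP gives up part of that protection because it removes patients for things that happen after assignment. Here the patient and clinician know the assigned duration. Treatment may run past the window, or antibiotics may be added, because the patient is worse. Treatment may also stop early because the patient is well. A missed Visit 3 may be related to outcome too. If such exclusions differ between arms in number or in kind, the PP difference moves away from the ITT difference.

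As written, a PP pass with an ITT fail would count as non-inferiority of 10 days. The open list of violations adds a smaller problem: PP membership is not fully fixed in advance, and no outcome-blind adjudication before data lock is described.

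**Working it through.** **The plan's own figure.** Protocol 15.7 gives 155 completers per arm, SD 9.0, margin 3.5, true difference 0 and 93% power. SE = 9 × √(2/155) = 1.022. Power = Φ(3.5/1.022 − 1.96) = Φ(1.46) = 92.8%, so the figure reproduces. The protocol's two-sided 0.05 and the SAP's one-sided 0.025 use the same critical value.

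**Bias formula.** Let f be the share of an arm excluded from PP, and D the mean FEV₁ change of retained patients minus that of excluded patients in the same arm. The whole-arm mean equals the retained mean − f × D. Hence

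PP difference = ITT difference + (f10 × D10 − f14 × D14).

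The bias is zero when the two products match. Equal exclusion rates alone are not enough.

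**Error of the PP test at a true deficit of exactly 3.5.** Error = Φ(bias/SE − 1.96), with SE = 9 × √(1/[155(1−f10)] + 1/[155(1−f14)]). The values of f and D are assumptions. D of 8.5 is the gap between the pilot means in Protocol 15.7 (12.5 − 4.0), and D of 12.5 means the whole pilot gain is lost.

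| f10 / f14 | D10 / D14 | Bias | SE | Error |
|---|---|---|---|---|
| 10% / 10% | 8.5 / 8.5 | 0 | 1.078 | 2.5% |
| 10% / 10% | 12.5 / 8.5 | +0.40 | 1.078 | 5.6% |
| 10% / 10% | 8.5 / 12.5 | −0.40 | 1.078 | 1.0% |
| 10% / 5% | 2 / 2 | +0.10 | 1.063 | 3.1% |
| 10% / 5% | 5 / 5 | +0.25 | 1.063 | 4.2% |
| 10% / 5% | 8.5 / 8.5 | +0.425 | 1.063 | 5.9% |
| 10% / 5% | 12.5 / 12.5 | +0.625 | 1.063 | 8.5% |
| 15% / 5% | 2 / 2 | +0.20 | 1.079 | 3.8% |
| 15% / 5% | 8.5 / 8.5 | +0.85 | 1.079 | 12% |
| 15% / 5% | 12.5 / 12.5 | +1.25 | 1.079 | 21% |
| 5% / 10% | 8.5 / 8.5 | −0.425 | 1.063 | 0.9% |
| 5% / 10% | −5 / −5 | +0.25 | 1.063 | 4.2% |

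In the last two rows the excess is in ERR-14 both times, yet the bias has opposite signs. Which arm loses more patients does not settle the direction.

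**Requiring both sets.** Simulated at a true deficit of 3.5 and D 8.5, with complete Visit 3 data and no rescue effect, the error is 2.3% (10/5) and 2.4% (15/5), against 5.8% and 12.0% for PP alone.

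The rule has two limits:

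- *Rescue.* If rescue treatment restores all of the excluded patients' deficit by Visit 3, and the true deficit is defined without rescue, the both-sets error is 4.7% (10/5) and 9.9% (15/5) at D 8.5. At D 12.5 (15/5) it is 18%, against 21% for PP alone.
- *Missing Visit 3.* Suppose ITT used complete cases. With 155/0.96 ≈ 161 randomized per arm, 6% versus 2% missing (average 4%, the drop-out rate in Protocol 15.7) and D 8.5, bias = 0.04 × 8.5 = 0.34 and SE = 1.024, so error = Φ(0.34/1.024 − 1.96) = 5.2%. Missed spirometry also removes the patient from PP, so on this route the second set adds nothing.

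**Power cost (true difference 0, 10% excluded per arm, simulated).**

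| Per arm | Exclusions | PP alone | Both sets |
|---|---|---|---|
| 155 | unrelated to outcome | 89.7% | 88.7% |
| 155 | D 8.5 | 90.0% | 87.5% |
| 198 | D 8.5 | 95.6% | 94.3% |

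The 198 per arm is the plan's own projection: 1236 × 1/3 × 0.96 ≈ 396 ERR completers.

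**The case against.** PP as primary for non-inferiority is a recognised convention, specified consistently in both documents. It has a reason: if ERR-10 patients drift toward 14 days, ITT is pulled toward no difference. This stands, and it is why the proposal adds ITT and keeps PP.

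The large error figures need large gaps. The 8.5 compares early responders with other patients, not excluded with retained patients within ERR. Every ERR patient had already gained at least 8 points by Visit 2, and some violations, such as eligibility failures, need not track outcome. This also stands, so the small-D rows deserve equal weight.

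The plan would expose discordance. Non-adherent patients are not withdrawn and remain in ITT (Protocol 12.1, 15.1). Feasibility by arm is scheduled semi-annually and at 10%, 20% if needed, 50% and 75% enrollment (SAP 1.2). Withdrawals and duration adherence are tabulated by arm, and prohibited antibiotic use is summarised (SAP 2.2). Secondary analyses use both sets (Protocol 15.4), and patients lost to follow-up are compared with completers (SAP 2.12). All true, but visibility is not a decision rule.

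A reader might infer that the plan tilts the trial toward non-inferiority, or that its real error rate is 12% to 21%. The documents support neither. They give no exclusion rates or outcome gaps, and D can be negative. A reader might also infer that ITT is ignored, but it is a prespecified repeat analysis.

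**Conclusion.** The point holds as a cheap improvement to a conventional plan. What is established from the text is a gap: PP decides, ITT is repeated, and nothing says what follows if they disagree. That PP exclusions can be outcome-related follows from Protocol 13 and the open-label design. Whether they will be, in which direction and by how much, cannot be derived.

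The illustrated error runs from 0.9% to 21% against a nominal 2.5%. It rests on assumed f and D, SD 9 and 155 per arm. It shows sensitivity and is not an estimate of this trial's error.

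The both-sets rule cannot raise the error above that of PP alone, because it only adds a condition. It does not fully control error when rescue restores FEV₁ by Visit 3, and it gives no protection when Visit 3 is missing.

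**What to change.** In Protocol 15.1 and 15.3 and SAP 1.4 and 2.5, state that ERR non-inferiority is declared only if the lower 95% limit for ERR-10 minus ERR-14 is above −3.5 in both PP and ITT. No alpha split is needed, since both tests must pass.

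Supporting steps:

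- State in the SAP the ITT missing-data method that Protocol 15.1 defers to it. One option is multiple imputation from Visit 1 and Visit 2 FEV₁ and the strata, with a tipping-point shift of missing ERR-10 values.
- Fix a closed list of PP-excluding violations before data lock, without knowledge of outcome.
- Reconcile Protocol 7.2, which names oral or inhaled antibiotics, with 8.2, which adds IV, so that it is clear whether IV retreatment before Visit 3 removes a patient from PP.

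An ITT analysis scoring retreated or extended patients as having no gain is optional and supportive only. It asks a different question, and its own error is 5.1% when exclusions are balanced at 10% per arm (D 8.5).

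The cost is wording plus about 1 to 2.5 points of power at 155 per arm with 10% excluded per arm, or 95.6 − 94.3 = 1.3 points at 198 per arm (D 8.5). Protocol 15.3 has the SAP finalized before data lock, which leaves room for the change. Patient care is unaffected.

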15.2 Demographic and Baseline Characteristics

Treatment duration arms (ERR-10, ERR-14, NERR-14, NERR-21) within ERR and NERR groups will be described and compared with respect to Baseline demographic and clinical characteristics including age, sex, CFTR genotype, race, height, weight, and all randomization strata. For all analyses, Baseline clinical characteristics will be defined as measurements obtained at Visit 1.

15.3 Analysis of Primary Endpoint

The primary endpoint is absolute change in percent predicted FEV₁ from Visit 1 (Baseline) to two weeks after scheduled completion of IV antibiotics (Visit 3). The primary endpoint will be compared between treatment durations within ERR and NERR groups using Analysis of Variance (ANOVA) adjusted for dichotomous randomization strata: Visit 1 FEV₁, number of IV-treated exacerbations in prior year, location of IV administration by Visit 2, and use of systemic corticosteroids by Visit 2.

The treatment effect for each group (ERR and NERR) (estimated via adjusted ANOVA least squares means) will be presented along with corresponding 95% confidence intervals. Observed treatment effect and the 95% CI will provide primary inference and evidence of non-inferiority, superiority, or lack thereof in both the ERR and NERR groups.

ERR Group: The non-inferiority of ERR-10 versus ERR-14 will be tested against a 3.5 % predicted non-inferiority margin with a two-sided 0.05 level of significance.

NERR Group: The superiority of NERR-21 versus NERR-14 will be tested with a two-sided 0.05 level of significance.

Further details will be provided in the SAP, which will be finalized before the clinical data lock for the study.

15.4 Analysis of Secondary Endpoints

Descriptive analyses and graphical displays will be used to summarize all secondary endpoints, including changes from baseline in continuous endpoints and rates over the follow-up period for event based endpoints. The ITT and PP populations will be used for all secondary analyses.

All reported SAEs and AEs will be coded using MedDRA and grouped by body system. (S)AEs will be tabulated by treatment durations within ERR and NERR groups using standard coding terms sorted by body system. The incidence of AEs (including emergent abnormal lab values collected for clinical care) in each treatment duration arm will be tabulated by seriousness, severity, and relationship to arm. If an AE is reported more than once during the study period for a given subject, the greatest severity and the worst-case relationship will be presented in tables. The number of (S)AEs will be summarized by treatment duration arms within ERR and NERR groups as follows: (i) The proportion of subjects with at least one (S)AE, (ii) The average number of (S)AEs per patient, and (iii) The rate of (S)AEs per patient month of follow-up. Histograms showing the frequency of the number of (S)AEs in each treatment duration arm will be included. Rates of (S)AEs by System Organ Class (SOC) will be presented by treatment duration arm. Poisson regression modeling will be used to derive rate ratios and 95% confidence

intervals for each SOC. The rate ratios will be compared using a two-sided 0.05 level test for Poisson count data.

Descriptive summaries of antibiotics received by patients will be presented by treatment duration arm within ERR and NERR groups. Proportion of patients retreated with IV antibiotics (as collected in the CFFNPR) for pulmonary exacerbation within 30 days following scheduled completion of IV antibiotic treatment will be summarized by treatment duration arm within ERR and NERR groups and differences in the proportion of subjects will be estimated and tested using a two-sided test of proportions. Time (days) to next exacerbation following scheduled completion of IV antibiotics will be presented using Kaplan-Meier survival estimation and compared between treatment durations within ERR and NERR groups using a Cox proportional hazards model with a test of the treatment effect at a two-sided significance level of 0.05. The hazard ratio and its 95% confidence interval will be presented. An additional secondary analysis may stratify by or adjust for the randomization strata.

Absolute change in CRISS, relative change in FEV₁ (liters), and absolute change in weight (kg) from Baseline (Visit 1) to two weeks after scheduled completion of IV antibiotics (Visit 3) will be summarized. Mean differences between treatment duration arms within ERR and NERR groups at each visit and corresponding 95% CIs will be presented. Changes from Baseline (Visit 1) to Visit 3 will be assessed using a two-sample, two-sided t-test and additional secondary analysis may adjust for the randomization strata.

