7.2 Prohibited Medications and Treatments

No antibiotics (oral or inhaled) should be taken following the scheduled completion of the IV treatment of PEx until after Visit 3 except as noted in Section 7.1.1 (above).

Investigational therapies are prohibited during the study. The combination modulator ivacaftor/tezacaftor or a triple combination therapy is not considered an investigational therapy and those subjects who are on an open label extension or an Expanded Access Program will be considered eligible for STOP2 as long as it is part of a stable regimen (i.e., >30 days of treatment).

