8.2 Antibiotic Selection

Initial IV antibiotics will be selected using study-specific guidelines provided and taking into account prior sputum culture results, previous antibiotic intolerances, and known drug allergies. Antibiotics may be changed at Visit 2 if presumed to be an insufficient response, sooner if there is a rapid decline, new intolerance or drug allergy. Such changes should still adhere to the study-specific guidelines and may represent newly identified pathogens in sputum cultures. If an antibiotic change is made due to insufficient response, the decision to change should be made prior to randomization at Visit 2.

Once the subject has completed the assigned IV antibiotic duration, no additional oral, inhaled, or IV antibiotics should be administered, except as specified in Section 7.1 above.

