2.6 Summary of Antibiotics and Other Medications

Descriptive summaries of antibiotics received by participants are presented by treatment duration arm within ERR and NERR groups. Also summarized is the use of steroids or airway clearance any time during the study. Proportion of patients retreated with IV antibiotics (as collected in the CFFNPR) for pulmonary exacerbation within 30 days following scheduled completion of IV antibiotic treatment is summarized by treatment duration arm within ERR and NERR groups and differences in the proportion of subjects are estimated and tested using a two-sided test of proportions.

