2.7 Time to Next Pulmonary Exacerbation

Time (days) to next exacerbation following scheduled completion of IV antibiotics is presented using Kaplan-Meier survival estimation and compared between treatment durations within ERR and NERR groups using a Cox proportional hazards model with a test of the treatment effect at a two-sided significance level of 0.05. The hazard ratio and its 95% confidence interval are presented. Additionally, results from a model adjusted for randomization strata are shown. Also performed are exploratory analyses testing proportion of time spent receiving home IVs and the timing of corticosteroid initiation.

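### The per-protocol versions of 30-day retreatment and time to next exacerbation can exclude patients because they had the event; make ITT the lead population for these two endpoints.

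*Protocol*

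**What the plan says.** Protocol 15.4 sets the populations in one sentence: "The ITT and PP populations will be used for all secondary analyses". Two of the secondary efficacy endpoints in Protocol 5.2 count relapse from the scheduled end of IV treatment: the proportion retreated within 30 days and the time to the next exacerbation. SAP 2.6 reports the first as retreatment "within 30 days following scheduled completion of IV antibiotic treatment is summarized by treatment duration arm". SAP 2.7 covers the second: "Time (days) to next exacerbation following scheduled completion of IV antibiotics is presented using Kaplan-Meier survival estimation". Neither section names a population. SAP 1.4 assigns populations to compliance, safety and primary efficacy, but not to secondary efficacy.

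The PP set is "defined as subjects in the ITT population who have no protocol violations as defined in Section 13" (Protocol 15.1). Section 13 gives a list that is expressly not exhaustive, and it includes "Use of a prohibited concomitant medication".

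Two sections restrict antibiotics after the assigned course, and they differ. Section 7.2, on prohibited medications, reads "No antibiotics (oral or inhaled) should be taken following the scheduled completion of the IV treatment of PEx until after Visit 3", apart from the chronic therapies allowed in 7.1.1. Section 8.2 reads "no additional oral, inhaled, or IV antibiotics should be administered, except as specified in Section 7.1 above". Section 7.2 does not name IV antibiotics and section 8.2 does. Neither makes an exception for treating a relapse. Visit 3 falls 14 days (±2) after the scheduled end of IV treatment.

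**The concern.** Membership of the PP set depends on what happens after randomisation. For FEV1 that is the usual price of a PP analysis. For a retreatment endpoint the excluding event can be the outcome itself. The PP result then describes retreatment among patients who reached Visit 3 without being treated for a relapse, which is not the comparison of durations that the endpoint was chosen to make.

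Protocol 2.1 names early relapse as the potential risk of too short a course. The days just after treatment stops are where that risk would show, and they are the days the PP versions can lose. Both endpoints are formally tested between arms, and nothing says which population leads for them.

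**Working it through.** The plan states no figure for these endpoints, so there is none to reproduce. The check first traces the definitions and then sizes the effect under stated assumptions.

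**Definitions**

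1. 15.4 sends both endpoints to PP as well as ITT. SAP 2.6 and 2.7 do not withdraw this.
2. 15.1 removes any Section 13 violation from PP, and prohibited medication is one.
3. *8.2 reading.* If 8.2 is part of the prohibition, or falls under Section 13's open-ended list, every IV retreatment before Visit 3 removes the patient. Section 8.2 gives no end date, so I take Visit 3, as in 7.2. The PP Kaplan-Meier curve is then flat for about the first 12 to 16 days.
4. *7.2 reading.* Only patients who also took a new oral or inhaled antibiotic are removed.

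**Assumptions** (no retreatment rates are in the documents)

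- True 30-day retreatment p is 15% in one arm and 8% in the other, a difference of 7.0 points.
- The hazard is constant and Visit 3 is on day 14. A uniform spread would put 14/30 = 47% of the window before Visit 3 (12/30 = 40% to 16/30 = 53% over the visit window).

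**Formulas**

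- Risk of an event before Visit 3: e = 1 − (1 − p)^(14/30).
- PP proportion: (p − g·e)/(1 − g·e), where g is the share of early relapses that lead to exclusion. On the 8.2 reading g = 1. On the 7.2 reading g lies between 0 and 1 and is unknown.

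**8.2 reading, g = 1**

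- p = 15%: e = 1 − 0.85^(14/30) = 7.30%; PP = (15 − 7.30)/(100 − 7.30) = 8.30%.
- p = 8%: e = 1 − 0.92^(14/30) = 3.82%; PP = (8 − 3.82)/(100 − 3.82) = 4.35%.
- PP difference = 8.30 − 4.35 = 3.95 points, against 7.0 in ITT. The loss is 1 − 3.95/7.0, about 44%.
- At the planned 155 ERR completers per arm, about 155 × 7.30% = 11.3 and 155 × 3.82% = 5.9 patients with events would be removed.

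If 70% of events in both arms fell before Visit 3, PP would be 4.5/89.5 = 5.03% v 2.4/94.4 = 2.54%. The difference is 2.49 points, a loss of about 64%.

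**7.2 reading, for illustration g = 0.5**

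- (15 − 3.65)/(100 − 3.65) = 11.78% and (8 − 1.91)/(100 − 1.91) = 6.21%.
- The difference is 5.57 points, a loss of about 20%. As g goes to 0 the loss goes to 0.

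**Relative measures, 8.2 reading, constant hazard**

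- Hazard ratio before removal: ln(0.85)/ln(0.92) = 1.95. After removal: ln(0.9170)/ln(0.9565) = 1.95.
- Risk ratio before: 15/8 = 1.88. After: 8.30/4.35 = 1.91.

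Removing everyone with an event before day 14 acts as a day-14 landmark. Under this model the ratios hold and only events, hence precision, are lost.

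**Early relapses concentrated in one arm**

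Assume 10% v 5% at 30 days, with 70% of events early in the first arm and 30% in the second. PP gives 3.0/93.0 = 3.2% v 3.5/98.5 = 3.6%. A 5.0-point excess becomes −0.3 points, and the relative measures fail as well.

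**The case against.** The case for leaving the plan alone is substantial, and most of it stands.

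- *ITT is also run.* A reader might infer that early relapses disappear from the trial's results. They do not: 15.4 requires the ITT version of both endpoints, and it counts every event. Events between Visit 3 and day 30 also stay in PP unless the patient has another violation.
- *Retreatment before Visit 3 is already protected.* A reader might include it among the affected endpoints. Protocol 5.2 lists it under safety, SAP 2.4 reports it there, and SAP 1.4 puts all safety analyses in ITT.
- *Exclusion for IV retreatment alone is an inference.* The section on prohibited medications names only oral and inhaled antibiotics. Reaching IV needs 8.2, a sentence under antibiotic selection, or Section 13's open-ended wording. SAP 2.2 reports prohibited antibiotic use under compliance, while SAP 2.4 treats retreatment as a safety measure. That weakens the 8.2 reading without excluding it, because no text exempts retreatment.
- *Not every measure is pulled toward no difference.* Under constant hazards the Cox hazard ratio, which is the planned measure for time to next exacerbation, does not move. Only the absolute 30-day difference shrinks.
- *PP leads only for the primary ERR analysis.* A reader might take this point as a flaw in the FEV1 non-inferiority result. The documents give PP no priority for any secondary endpoint, and this point does not bear on FEV1.

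What the objection does not remove is that, under either antibiotic section, a relapse can take a patient out of an analysis meant to count relapses, and no passage says which version leads.

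**Conclusion.** The point holds in a limited form. The PP versions of 30-day retreatment and time to next exacerbation are selected on the outcome. On the 8.2 reading they lose all events in about the first 14 days. On the 7.2 reading they lose only relapses also given a new oral or inhaled antibiotic.

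Under the assumed 15% v 8% and constant hazard, the 8.2 reading cuts the absolute 30-day difference from 7.0 to about 4.0 points. The 7.2 reading cuts it by less, in proportion to a share that the documents do not give. The hazard ratio loses precision and is biased only if early relapses are concentrated in one arm. All rates and early shares here are assumptions.

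Severity is minor because the ITT versions are unaffected and will be reported. The correction is a cheap improvement.

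**What to change.** In SAP 1.4, 2.6 and 2.7, make ITT the sole or lead population for 30-day retreatment and time to next exacerbation. If a PP version is kept, state that for these two endpoints antibiotics started for respiratory worsening after the scheduled end of IV treatment do not remove a patient from the set. Retreatment before Visit 3 needs no change.

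Reconcile Protocol 7.2 with 8.2 on whether IV antibiotics are covered, so that violations are coded in one way. This review takes no position on what the clinical rule should be.

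The cost is one or two sentences in the SAP and a clarification in the protocol, with no new data or patients. The downside is that the PP set for these endpoints would differ slightly from the PP set for FEV1, which the tables should label.
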